5.2. Exclusion criteria

...

[27] Have active TB (refer to Section 8.2.78.2.6 for details on determining full TB exclusion criteria).

...

[32] ...

Note: Patients who are negative for hepatitis B surface antigen (HBsAg-), HBcAb+, HBsAb+ with a concentration of HBsAb ≥ 200 mIU/mL, and negative for serum HBV DNA may participate in the study. Patients who meet these criteria at screening will be identified by the central laboratory and monitored during the study as detailed in Section 8.2.8.18.2.7.1.

5.4. Screen Failures

...

- Patients who test positive for latent TB at screening and have undergone documented subsequent treatment for at least 4 weeks (more details in Section 8.2.67).

...

6.1. Study Intervention(s) Administered

Table RHCZ.6.1. Treatment Regimens

Treatment Group	Starting Dose W0	Dose W2-W10	Dose ^a W12-W20
Ixekizumab for 
 PsO participants with no active PsA and PsA participants who meet criteria for moderate-to-severe PsO 	Ixekizumab 80 mg × 2 SC (total of 160 mg)	Ixekizumab 80 mg SC Q2W at W2, 4, 6, 8, and 10	Ixekizumab 80 mg SC Q4W at W12, W16 and 20
Ixekizumab for PsA participants who do not meet criteria of for for moderate-to-severe PsO	Ixekizumab 80 mg × 2 SC (total of 160 mg)		Ixekizumab 80 mg SC Q4W at W4, 8, 12, 16 and 20.

Abbreviations: PsA = psoriatic arthritis; PsO = psoriasis; Q2W = every 2 weeks; Q4W = every 4 weeks; SC = subcutaneous injection; W = week.

^a No dose is given at W24; therefore, W24 is not included in this table.

Note: When the dosing is scheduled at home (for PsO participants with no active PsA and PsA participants who meet criteria for moderate-to-severe PsO: W2, W6, W10, W16, and W20; for PsA participants who do not meet criteria ~~of for~~ for moderate-to-severe PsO: W16 and W20), the participants or care givers will self-administer the provided ixekizumab prefilled syringes.

...

During study visits, the investigator or his/her designee will administer the ixekizumab prefilled syringes to the participant. When the dosing is scheduled at home, the participants or care givers will self-administer the provided ixekizumab prefilled syringes.

...

Induction Dosing Period (Period 2) (Table RHCZ.6.2)

- At Week 0, a 160-mg starting dose of ixekizumab (two 80-mg injections), followed by ixekizumab 80 mg Q2W from Weeks 2 through 12 for PsO participants with no active PsA and PsA participants who meet criteria for moderate-to-severe PsO.
- At Week 0, a 160-mg starting dose of ixekizumab (two 80-mg injections), followed by ixekizumab 80 mg Q4W from Weeks 4 through 12 for PsA participants who do not meet the criteria for moderate-to-severe without PsO participants.

...

Table RHCZ.6.2. Dosing Summary for the Induction and Maintenance Periods

Dosing Period	Study Week	Ixekizumab Treatment Group ^a	
		Ixekizumab (80 mg)	
		PsO Participants with no active PsA and PsA Participants Who Meet Criteria for Moderate-to-Severe PsO with or without PsA Participants^b	PsA Participants Who Do Not Meet Criteria for Moderate-to-Severe PsO PsA without PsO Participants^c
Induction Dosing Period 2	0	2 ^a	2 ^a
	2	1	-
	4	1	1
	6	1	-
	8	1	1
	10	1	-
	12	1	1
	16	1	1
Maintenance Period 3	20	1	1
	24	-	-

Abbreviations: PsA = psoriatic arthritis; PsO = psoriasis; Q2W = every 2 weeks; Q4W = every 4 weeks; Q8W = every 8 weeks; SC = subcutaneous.

^a A starting dose of 160 mg (Week 0) of ixekizumab will be given as 2 SC injections at Week 0.

^b For PsO participants with no active PsA and PsA participants who meet criteria for moderate-to-severe PsO, during the Induction Dosing Period, ixekizumab (80 mg) will be given as 1 SC injection Q2W (i.e., Weeks 2, 4, 6, 8, 10, and 12). During the Maintenance Period, ixekizumab (80 mg) will be given as 1 SC injection Q4W (i.e., Weeks 16 and 20).

^c For PsA participants who do not meet criteria or for moderate to severe PsO, ixekizumab (80 mg) will be given as 1 SC injection Q4W (i.e., Weeks 4, 8, 12, 16, and 20).

6.8. Concomitant Therapy

All concomitant medication taken during the study must be recorded on the Concomitant Medication CRF at the study visits indicated in the SoA (Section 1.3). Treatment with concomitant PsO and PsA therapies during the study will be permitted only as outlined in the inclusion and exclusion criteria (Sections 5.1 and 5.2, respectively) and as described in the paragraphs below. Participants taking permitted medications need to be documented to be in stable control. After trial enrollment, significant dose escalation of a concomitant medication should be discussed with Lilly medical before allowing participant to receive study intervention.

...

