- [42] Have received systemic non-biologic PsO therapy (including, but not limited to, oral psoralens and ultraviolet A [PUVA] light therapy; cyclosporine; corticosteroids; methotrexate [MTX]; oral retinoids; mycophenolate mofetil; thioguanine; hydroxyurea; sirolimus; azathioprine; fumaric acid derivatives; or 1,25 dihydroxy vitamin D3 and analogues) or phototherapy (including either oral and topical PUVA light therapy, ultraviolet B [UVB] or self-treatment with tanning beds or therapeutic sunbathing) within 4 weeks prior to baseline (Week 0; Visit 2); or had topical PsO treatment (including, but not limited to, corticosteroids, anthralin, calcipotriene, topical vitamin D derivatives, retinoids, tazarotene, emollients and other non-prescription topical products containing urea, >3% salicylic acid, or alpha- or beta-hydroxyl acids, and medicated shampoos [e.g., those that contain >3% salicylic acid, corticosteroids, coal tar, or vitamin D3 analogues]) within the previous 2 weeks prior to baseline (Week 0; Visit 2).

Exceptions: class 6 (mild, such as desonide) or class 7 (least potent, such as hydrocortisone) topical steroids will be permitted for use limited to the face, axilla, and/or genitalia.

- [43] Have pustular, erythrodermic, and/or guttate forms of PsO.
- [44] Had a clinically significant flare of PsO during the 12 weeks prior to baseline (Week 0; Visit 2).
- [45] Have allergy to rubber or latex.

PsA Participants

- [46] Have used conventional synthetic disease-modifying antirheumatic drug (csDMARDs) other than MTX, leflunomide, sulfasalazine, or cyclosporine in the 8 weeks prior to baseline (Week 0; Visit 2).

Have discontinued MTX, sulfasalazine, or cyclosporine within 12 weeks prior to baseline (Week 0; Visit 2).

If taking MTX, leflunomide, sulfasalazine, or cyclosporine, must have been treated for at least 12 weeks prior to baseline *and* on a stable dose for at least 8 weeks prior to baseline, as follows: oral or parenteral MTX = 10 to 25 mg/week; leflunomide = 20 mg/day; sulfasalazine = up to 3 g/day; or cyclosporine up to 5 mg/kg/day. The dose of these allowed concomitant medications must remain unchanged during the study periods of the unless changes are required for safety issues. Local standard of care should be followed for concomitant administration of folic acid with MTX.

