6.8. Concomitant Therapy

All concomitant medication taken during the study must be recorded on the Concomitant Medication CRF at the study visits indicated in the SoA (Section 1.3). Treatment with concomitant PsO and PsA therapies during the study will be permitted only as outlined in the inclusion and exclusion criteria (Sections 5.1 and 5.2, respectively) and as described in the paragraphs below. Participants taking permitted medications need to be documented to be in stable control. After trial enrollment, significant dose escalation of a concomitant medication should be discussed with Lilly medical before allowing participant to receive study intervention.

Table RHCZ.6.3 summarizes concomitant medications that are and are not permitted and their conditions for use during the study.

Table RHCZ.6.3. Concomitant Medications Permitted/Not Permitted in the Study and Conditions for Use

Drug Class	Permitted/Not Permitted during the Trial	Conditions for Use
Bath oils and oatmeal bath preparations	Permitted	Not to be used within 12 hours of a study visit.
NSAIDs, acetaminophen, or aspirin	Permitted	Allowed as needed.
Shampoos	Permitted	May not contain >3% salicylic acid, corticosteroids, coal tar, or vitamin D3 analogues. Not to be used within 12 hours of a study visit.
Topical moisturizers/emollients and other non-prescription topical products	Permitted	Do not contain urea, >3% salicylic acid, alpha- or beta-hydroxyl acids, corticosteroids, or vitamin D3 analogues. Not to be used within 12 hours of a study visit.
Topical steroids		
Mild (such as hydrocortisone)	Permitted	Permitted for use limited to the face, axilla, groin, and/or genitalia, as needed. These topical medications should not be used within approximately 24 hours before study visits requiring sPGA and PASI measures. More widespread use on large surfaces is not permitted.
Strong (such as mometasone), very strong (betamethasone) ^a , and halogenated steroids (clobetasone)	Not permitted	
Biologic agents other than study intervention as part of this protocol	Not Permitted	Washout periods before baseline (Week 0, Visit 2); at least 5 half-lives

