IL-17, IL-23p19 antagonists, other than the 2 products used as part of this protocol.	Not permitted	Must have never received ixekizumab or IL-23p19 antagonists; or participated in any study investigating IL-23p19 antagonists. Participant with previous exposure to another IL-17 antagonist(s) will be limited to approximately 15% of the total participant population.
Natalizumab or other agents targeting α 4 integrin	Not permitted	Must have never received.
Phototherapy (including either oral and topical PUVA light therapy, UVB, or self-treatment with tanning beds or therapeutic sunbathing)	Not permitted	Must not have received within 4 weeks of baseline (Week 0, Visit 2).

Concomitant Medications Permitted/Not Permitted in the Study and Conditions for Use

Drug Class	Permitted/Not Permitted	Conditions for Use
Systemic nonbiologic psoriasis therapy (e.g., oral PUVA light therapy, cyclosporine, corticosteroids, MTX, oral retinoids, mycophenolate mofetil, thioguanine, hydroxyurea, sirolimus, azathioprine, fumaric acid derivatives, apremilast, and 1,25 dihydroxy vitamin D3 and analogues)	Not permitted (for PsO participants) Permitted (for PsO participants who met PsA criteria and PsA participants) with conditions	Must not have received within 4 weeks of baseline (Week 0, Visit 2). Stable dose allowed. Stable doses with no dose adjustments, changes, and/or introduction of a new csDMARD Allowed doses: 
 • Oral or parenteral MTX; 10 to 25 mg/week • Leflunomide: up to 20 mg/day • Sulfasalazine: up to 3 g/day • Cyclosporine: up to 5 mg/kg/day
Vaccine, Bacillus Calmette-Guérin	Not permitted	Must not have received within 12 months of baseline (Week 0, Visit 2). Should not receive within 12 months of completed treatment in this study.
Vaccines, live	Not permitted	Must not have received within 12 weeks of baseline (Week 0, Visit 2). Should not receive within 15 weeks of completed treatment in this study.
Vaccines, non-live seasonal and/or emergency	Permitted with conditions	Killed/inactive, RNA vaccine, or subunit vaccines are expected to be safe; however, their efficacy with concomitant ixekizumab treatments is unknown. Check with Lilly Medical Team (CRS/CRP) before administration.

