Abbreviations: CRS/CRP = clinical research scientist/clinical research physician; csDMARD = conventional synthetic disease-modifying antirheumatic drug; IL = interleukin; MTX = methotrexate; NSAID = nonsteroidal anti-inflammatory drug; PASI = Psoriasis Area and Severity Index; PsA = psoriatic arthritis; PsO = plaque psoriasis; PUVA = psoralen and ultraviolet A; RNA = ribonucleic acid; sPGA = static Physician Global Assessment; UVB = ultraviolet B.

^a Mason et al. 2002.

Additional drugs are to be avoided during the study unless required to treat an AE or for the treatment of an ongoing medical problem. If the need for concomitant medication arises, the investigator should base decisions on the participant and clinical factors. Any additional medication (including the limited use of therapeutic agents which, if used under treatment regimens other than for treating an AE or for appropriate medical management, might be considered PsO/PsA therapies) whether prescription or over-the-counter, used at baseline (Week 0, Visit 2) and/or during the course of the study, must be documented with the start and stop dates on the Concomitant Medications CRF.

Participants will maintain their usual medication regimen for other concomitant diseases throughout the study unless those medications are specifically excluded in the protocol.

Participants taking concomitant medications should be on stable doses at the time of baseline (Week 0, Visit 2) and should remain at a stable dose throughout the study, unless changes need to be made for an AE or for appropriate medical management. Other medications may be allowed if approved by the Sponsor or its designee.

Participants should be instructed to consult the investigator or other appropriate study personnel at the site before taking any new medications or supplements. Any changes in medications not addressed above should be discussed by the investigator with the Sponsor.

7. Discontinuation of Study Intervention and Participant Discontinuation/Withdrawal

Discontinuation of specific sites or of the study as a whole are handled as part of Section 10.1, Section 10.1.7.

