7.2. Participant Discontinuation/Withdrawal from the Study

A participant may withdraw from the study:

- at any time at the participant's own request;
- at the request of the participant's designee (e.g., parents or legal guardian);
- at the discretion of the investigator for safety, behavioral, compliance, or administrative reasons;
- if enrolled in any other clinical study involving an investigational product, or enrolled in any other type of medical research judged not to be scientifically or medically compatible with this study;
- if participation in the study needs to be stopped for medical, safety, regulatory, or other reasons consistent with applicable laws, regulations, and good clinical practice (GCP) or
- if the participant, for any reason, requires treatment with a therapeutic agent that is prohibited by the protocol and has been demonstrated to be effective for treatment of the study indication. In this case, discontinuation from the study occurs prior to introduction of the new agent.

Discontinuation is expected to be uncommon.

At the time of discontinuing from the study, if possible, an ETV should be conducted, as shown in the SoA (Section 1.3). See the SoA for data to be collected at the time of study discontinuation and follow-up and for any further evaluations that need to be completed. The participant will be permanently discontinued both from the study intervention and from the study at that time.

If the participant withdraws consent for disclosure of future information, the Sponsor may retain and continue to use any data collected before such a withdrawal of consent. If a participant withdraws from the study, the participant may request destruction of any samples taken and not tested, and the investigator must document this in the site study records.

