9.3.1 General Nonresponder Imputation for Clinical Response

Analysis of categorical efficacy and health outcomes variables will be assessed using a nonresponder imputation (NRI) method. Participants will be considered a nonresponder for the NRI analysis if they:

- do not meet the clinical response criteria (e.g., ACR20, PASI75, PASI90, PASI100, sPGA [0,1]);
- have missing clinical response data at a timepoint of interest (e.g., Week 12, Week 24);
- discontinue study treatment at any time prior to a timepoint of interest for any reason; or
- have no postbaseline observation.

The NRI may be applied at any time point specified for analysis.

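### The protocol's rules on changing background csDMARD doses in PsA participants conflict, and the nonresponder rule does not say how Week 24 ACR20 treats such a change

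*Protocol*

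**What the plan says.** Five places in the Protocol govern changes in background therapy for PsA participants.

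- **Section 6.8, opening paragraph**, on any concomitant medication: "After trial enrollment, significant dose escalation of a concomitant medication should be discussed with Lilly medical before allowing participant to receive study intervention".
- **Table RHCZ.6.3, systemic nonbiologic row**, for PsA participants: "Stable doses with no dose adjustments, changes, and/or introduction of a new csDMARD". The row gives no exception and no end date. It lists permitted dose ranges, for example methotrexate 10 to 25 mg/week.
- **Section 6.8, closing text**, on concomitant medications in general: participants "should remain at a stable dose throughout the study, unless changes need to be made for an AE or for appropriate medical management".
- **Section 5.2, criterion [46]**, on methotrexate, leflunomide, sulfasalazine and cyclosporine: "The dose of these allowed concomitant medications must remain unchanged during the study periods of the unless changes are required for safety issues" (a word seems to be missing as printed).
- **Section 5.2, criterion [49]**, on methotrexate, leflunomide, sulfasalazine and hydroxychloroquine: the dose is fixed only up to Week 12, again with a safety exception.

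Section 9.3.1 names ACR20 and lists four ways to be a nonresponder: the response criteria are not met, the response data are missing, study treatment has stopped ("discontinue study treatment at any time prior to a timepoint of interest for any reason; or"), or there is no postbaseline observation. Section 7.2 provides for leaving the study when a participant "requires treatment with a therapeutic agent that is prohibited by the protocol" and the agent is known to work in the indication. The exit comes before the new agent is started. ACR20 at Week 24 is the secondary endpoint for the PsA group (Sections 3 and 9.5.3).

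**The concern.** Two problems meet at one endpoint. First, a site cannot tell from the Protocol whether a csDMARD dose may be raised after Week 12, so practice may differ between sites. Second, the nonresponder rule takes no account of such a change, although the added drug acts on the same joints that ACR20 measures. The trial has a single arm, so no comparison can separate the effect of a raised csDMARD dose from that of ixekizumab.

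The treatment of similar participants is also uneven. One who needs a prohibited effective agent leaves and counts as a failure. One who receives more of a permitted agent can stay and count as a success.

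**Working it through.** **Step 1: the dose rules applied to one case.** Take a PsA participant on methotrexate within the permitted range whose dose is raised at Week 14 for medical management, not for safety.

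- Table RHCZ.6.3, csDMARD row: not allowed.
- Criterion [46]: not allowed, because the only exception is safety.
- Criterion [49]: outside the freeze, which ended at Week 12.
- Section 6.8, closing text: allowed, through the clause "unless changes need to be made for an AE or for appropriate medical management".
- Section 6.8, opening paragraph: if the increase is significant, the sponsor is consulted; the outcome is not fixed.

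Section 6.8 says that PsO and PsA therapies are governed by the entry criteria together with its own text. It therefore brings in both [46] and [49] and ranks none of the five. The two criteria overlap on methotrexate, leflunomide and sulfasalazine, so the difference in duration is a conflict about the same drugs. The freeze in [49] ends 24 − 12 = 12 weeks before the ACR20 time point.

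**Step 2: the same case under Section 9.3.1.** The participant meets ACR20 at Week 24, has data, is still on study treatment and has postbaseline observations. None of the four conditions applies, so the participant is a responder. Under Section 7.2, a participant needing a prohibited effective agent is discontinued from both study and treatment, and the third condition makes that participant a nonresponder.

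**Step 3: scale.** The only sample-size arithmetic in the Protocol (Section 9.7) reproduces: 150 + 100 = 250, and 250 × (1 − 0.10) = 225 completers. It is not in dispute.

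For ACR20, n = 100 PsA participants (Section 9.7), with a normal-approximation CI (Section 9.5.3):

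- One participant reclassified: 1/100 = 1 percentage point.
- Half-width = 1.96 × √(p(1 − p)/n). At p = 0.50: 1.96 × √(0.25/100) = 9.8 points, the maximum. At p = 0.40 or 0.60 it is 9.6 points, and at 0.70 it is 9.0.

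**Step 4: illustration on assumed inputs.** The documents give neither an escalation frequency nor an expected ACR20 rate. Let p be the rate as coded now, e the share escalated and r the response rate among them. The recoded rate is p − e × r. With p = 50%:

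- e = 5%: 47.5% if r = 50%, 45.0% if r = 100%.
- e = 10%: 45.0% or 40.0%.
- e = 15%: 42.5% or 35.0%.

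Over p from 40% to 70% and e from 2% to 15%, with r between p and 100%, the shift runs from 0.02 × 0.40 = 0.8 points to 0.15 × 1.00 = 15 points. This is the size of the reclassification. Upward bias cannot exceed it, because some escalated responders would have met ACR20 on ixekizumab with their background dose unchanged.

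**The case against.** The strongest reply is that the specific rule governs. The csDMARD row bars dose changes, criterion [46] agrees except for safety, and the escalation sentence in Section 6.8 is then only a duty to contact the sponsor. That sentence covers any concomitant medication and does not say that escalation goes ahead. Its closing words could also refer to the first dose. These points stand as far as they go, and a reader should not infer that Section 6.8 expressly licenses escalation of PsA therapy on study drug. Nor does the whole table forbid dose changes: another row reads "NSAIDs, acetaminophen, or aspirin Permitted Allowed as needed". The conflict remains even so, because criterion [49] stops the freeze at Week 12, the closing text of Section 6.8 gives a wider exception than safety, and nothing sets an order among them.

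A second reply is that Section 9 is a summary, Section 9.5.3 leaves further ACR20 details to the SAP, and the mITT population keeps participants who depart from the protocol, which fits a treatment-policy approach. That approach would be legitimate if stated. Section 9.3.1 is silent on escalation and does not expressly credit it. But it does set out the nonresponder rule and names ACR20, and applied as written it has the result in step 2.

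A third reply is that new agents are already dealt with. This is largely right: the table bars a new csDMARD, and Section 7.2 covers prohibited effective agents. What remains is mainly an increase in a permitted agent.

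**Conclusion.** The point holds in limited form. The dose-change passages contradict each other for PsA participants, most plainly between Weeks 12 and 24, and Section 9.3.1 as written counts an escalated participant who meets ACR20 as a responder.

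The size is 1 percentage point per reclassified responder at n = 100, against a half-width of at most about 9.8 points. The total depends on an escalation frequency that the documents do not give.

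A reader might infer that the ACR20 rate is biased upward by a known amount, for example 1.5 to 10.5 points if 5 to 15 participants are escalated and 30% to 70% of them respond (5 × 0.3 = 1.5; 15 × 0.7 = 10.5). The documents do not support this. Those inputs are assumed, nothing shows that escalated participants are mainly poor responders, and the figures are an upper bound on bias.

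The consequence is also modest. ACR20 is a descriptive secondary endpoint in a single-arm safety study with no hypothesis test (Section 9.1), so no decision threshold depends on it.

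**What to change.** 1. Reconcile criteria [46] and [49], the csDMARD row of Table RHCZ.6.3, and the opening and closing text of Section 6.8, so that one rule on background dose changes applies, with one duration and one set of exceptions. Which rule that should be is for the sponsor and is not suggested here.
2. In Section 9.3.1, for Week 24 ACR20, count as a nonresponder any participant with a new or escalated csDMARD or systemic corticosteroid before the time point. At a minimum, report this as a sensitivity analysis beside the stated rule. In either case give the number reclassified.

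The cost is wording. Section 6.8 already requires concomitant medications to be recorded on the Concomitant Medication CRF, with start and stop dates for additional medications. The downside is a slightly lower ACR20 rate, or one more descriptive analysis.
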